6.5.5.2. Pregnancy Testing

A pregnancy test will be performed for females of child-bearing potential at the timepoints specified in the Schedule of Assessments ([Table 1](#) and [Table 2](#)).

A serum pregnancy test will be performed at Screening and urine pregnancy tests will be performed thereafter at the timepoints specified in the Schedule of Assessments ([Table 1](#) and [Table 2](#)). More frequent pregnancy testing may be performed where required per local requirements. The results of the pregnancy test must be known before study drug administration. Patients who are pregnant at Screening are not eligible for study participation. Any woman with a positive urine pregnancy test, subsequently confirmed by a positive serum pregnancy test, during the study will be discontinued from study drug but will continue to be followed for safety. Patients determined to be pregnant while on study will be followed at least until the pregnancy outcome is known (see Section [6.5.7.7](#) for follow-up instructions).

Follicle-stimulating hormone testing will be performed in all women suspected to be post-menopausal to confirm post-menopausal status.

6.5.6. Vital Status Check

A vital status check will be performed at the timepoints specified in the Schedule of Assessments ([Table 1](#) and [Table 2](#)).

Due to the inclusion of all-cause mortality in the secondary endpoint analysis, a medical records release form will be required of all patients for the purpose of obtaining vital status information from the patient's physician or from death registries. The signing of this medical records release form is in addition to the ICF. Also see Section [4.3.2.1](#) for the collection of vital status after withdrawal of consent and Section [4.3.3](#) for patients who are lost to follow-up.

6.5.7. Adverse Events

6.5.7.1. Definitions

Adverse Event

According to the International Council on Harmonisation (ICH) E2A guideline Definitions and Standards for Expedited Reporting, and 21 CFR 312.32, IND Safety Reporting, an AE is any untoward medical occurrence in a patient or clinical investigational subject administered a medicinal product and which does not necessarily have a causal relationship with this treatment.

Serious Adverse Event

An SAE is any untoward medical occurrence that at any dose:

- Results in death
- Is life-threatening (an event which places the patient at immediate risk of death from the event as it occurred. It does not include an event that had it occurred in a more severe form might have caused death)
- Requires inpatient hospitalization or prolongation of existing hospitalization
- Results in persistent or significant disability or incapacity
- Is a congenital anomaly or birth defect
- Is an important medical event that may not be immediately life-threatening or result in death or hospitalization but may jeopardize the patient and may require intervention to prevent one of the other outcomes listed in the definition above (eg, events include allergic bronchospasm requiring intensive treatment in an emergency room or at home, blood dyscrasias, convulsions, or the development of drug dependency or abuse).

Adverse Events of Clinical Interest

No AEs of clinical interest are defined for this study.

Adverse Event Severity

Adverse events are to be graded according to the categories detailed below:

- | | |
|-----------|---|
| Mild: | Mild; asymptomatic or mild symptoms; clinical or diagnostic observations only; intervention not indicated. |
| Moderate: | Moderate; minimal, local or noninvasive intervention indicated; limiting age appropriate instrumental activities of daily living (eg, preparing meals, shopping for groceries or clothes, using the telephone, managing money). |

Severe: Severe or medically significant but not immediately life-threatening; hospitalization or prolongation of hospitalization indicated; disabling; limiting self-care activities of daily living (ie, bathing, dressing and undressing, feeding self, using the toilet, taking medications, and not bedridden); OR life-threatening consequences; urgent intervention indicated; OR death related to an AE.

Changes in severity should be documented in the medical record to allow assessment of the duration of the event at each level of severity. AEs characterized as intermittent require documentation of the start and stop of each incidence. When changes in the severity of an AE occur more frequently than once a day, the maximum severity for the experience that day should be noted. If the severity category changes over a number of days, then those changes should be recorded separately (with distinct onset dates).

AE severity and seriousness are assessed independently. ‘Severity’ characterizes the intensity of an AE. ‘Serious’ is a regulatory definition and serves as a guide to the Sponsor for defining regulatory reporting obligations (see definition for SAE).

Relationship of the Adverse Event to Study Drug

The relationship of each AE to study drug should be evaluated by the Investigator by a “yes” or “no” response to the question: “Is there a reasonable possibility that the event may have been caused by the study drug?” A “yes” response indicates that the event is considered as related to the study drug.

6.5.7.2. Eliciting and Recording Adverse Events

Eliciting Adverse Events

The patient and legal guardian, if applicable, should be asked about medically relevant changes in the patient’s health since the last visit. The patient and legal guardian, if applicable, should also be asked if the patient has been hospitalized, had any accidents, used any new medications, or changed concomitant medication routines (both prescription and over-the-counter). In addition to patient observations, AEs will be documented from any clinically relevant laboratory findings, physical examination findings, ECG changes, or other findings that are relevant to patient safety.

Recording Adverse Events

The Investigator is responsible for recording non-serious AEs that are observed or reported by the patient after administration of the first dose of study drug regardless of their relationship to study drug through the end of study. Non-serious AEs will be followed until the end of study. Events occurring after signing of the ICF and before study drug administration will be captured as medical history (see Section 6.1), while AEs that occur after study drug administration, and baseline events that worsen after study drug administration, must be recorded as AEs.

The Investigator is responsible for recording SAEs that are observed or reported by the patient after the time when the informed consent is signed regardless of their relationship to study drug through the end of study. SAEs will be followed until satisfactory resolution, until baseline level

is reached, or until the SAE is considered by the Investigator to be chronic or the patient is stable, as appropriate.

All AEs must be recorded in the source records for the clinical study center and in the eCRF for the patient, whether or not they are considered to be drug-related. Each AE must be described in detail: onset time and date, description of event, severity, relationship to study drug, action taken, and outcome (including time and date of resolution, if applicable).

For SAEs, record the event(s) in the eCRF and, as applicable, the SAE form.

All IRRs will be recorded as AEs. All information on IRRs is to be recorded on the applicable eCRF per the CRF completion guidelines.

If patients develop ocular symptoms suggestive of vitamin A deficiency, for example reduced night vision or night blindness, the Investigator should consult with the Medical Monitor to determine if an ophthalmological assessment is needed. Any information collected during an ophthalmological assessment should be recorded in the eCRF and reports or images of ophthalmological assessments should be collected as well.

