For patisiran, important identified risks include IRRs. To minimize this risk, all patients must receive premedication with a corticosteroid, paracetamol/acetaminophen, and H1 and H2 blockers prior to patisiran administration (Section 5.2.1). The infusion may be interrupted or slowed if an IRR occurs (Sections 5.2.3 and 5.2.4). Important potential risks also include severe hypersensitivity (eg, anaphylaxis) to the active substance or any of the excipients. Patisiran is contraindicated in patients with a history of severe hypersensitivity (eg, anaphylaxis or anaphylactoid reactions) to patisiran or any of the excipients.

Vitamin A deficiency is also considered an important potential risk. Nonclinical and clinical data with patisiran have shown that the lowering of circulating vitamin A associated with the reduction in TTR (a carrier of retinol) does not result in vitamin A deficiency; transport and tissue uptake of vitamin A can occur through alternative mechanisms in the absence of retinol binding protein. However, as the vitamin A content of the diet may vary between different individuals, all patients will be instructed to take the recommended daily allowance of vitamin A while on the study (Section 5.3). Laboratory tests for serum vitamin A do not reflect the total amount of vitamin A in the body and should not be used to guide vitamin A supplementation beyond the recommended daily dose during treatment with patisiran.

Detailed information about the known and expected benefits and risks of patisiran may be found in the current edition of the Investigator's Brochure.

During the study, patients will be monitored, including evaluation of laboratory monitoring for liver function test abnormalities, renal function, and other standard hematology and blood chemistries. As the risk of embryofetal toxicity is currently unknown, females of child-bearing potential participating in the study must have a negative pregnancy test, cannot be breast feeding, and must be willing to use a highly effective method of contraception as specified in the protocol.

An external, independent Data Monitoring Committee (DMC) will monitor and ensure the safety of trial participants (see Section 3.7).

In conclusion, exploratory cardiac results from the APOLLO study suggesting that patisiran may halt or reverse the progression of the cardiac manifestations of hATTR amyloidosis [Solomon

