5.2.1. Premedication

All patients will receive premedication prior to study drug administration to reduce the risk of IRRs. Each of the following medicinal products should be given on the day of study drug infusion at least 60 minutes prior to the start of infusion:

- Intravenous corticosteroid (dexamethasone 10 mg or equivalent)
- Oral paracetamol (500 mg)
- Intravenous H1 blocker (diphenhydramine 50 mg, or equivalent)
- Intravenous H2 blocker (ranitidine 50 mg, or equivalent)

For premedications not available or not tolerated intravenously, equivalents may be administered orally.

If a patient is having difficulty tolerating the steroid premedication regimen (eg, patient develops uncontrolled hyperglycemia, altered mental status, or other complication), then lowering of the steroid premedication may be allowed for that patient after consultation with the medical monitor at any time during the study (double-blind and open-label periods).

In the open-label extension period only, for patients who are tolerating their drug infusions well with their current corticosteroid premedication regimen (ie, no IRRs during the past 3 or more infusions), corticosteroid dose may be reduced in 2.5 mg increments to a minimum dose of 5 mg of dexamethasone (IV) or equivalent.

Infusions during corticosteroid tapering (and the 2 infusions after the new and stable lower corticosteroid dose is established) should be performed in the clinic, as described in detail in the Pharmacy Manual.

Additional or higher doses of 1 or more of the premedications may be administered to reduce the risk of IRRs, if needed. For suggested guidelines for management of IRRs, see Section [5.2.4](#); further details can be found in the Pharmacy Manual.

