7.2.8. Safety Analyses

The primary parameter is the frequency of treatment-emergent AEs (hereafter referred to simply as AEs). Safety parameters also include vital signs, ECGs, clinical laboratory assessments and physical exams. The extent of exposure will be summarized.

Prior and concomitant medications will be coded using the World Health Organization Drug Dictionary. Results will be tabulated by the Anatomical Therapeutic Chemical classification system and Preferred Term (PT).

Adverse events will be classified according to the Medical Dictionary for Regulatory Activities (MedDRA) System Organ Class and Preferred Term. The frequency and percentage of patients experiencing AEs, SAEs, related AEs, and AEs leading to discontinuation will be summarized by System Organ Class (SOC) and PT. By patient listings will be provided for deaths, SAEs, and AEs leading to discontinuation.

Descriptive statistics will be provided for clinical laboratory data, ECG, and vital signs data, summarizing the observed values and change from baseline over time. Laboratory shift tables from baseline at the worst post-baseline values will be presented. Abnormal physical examination findings and 12-lead ECG data will be presented in by-patient listings.

Other safety summaries will be presented as appropriate. Further details will be specified in the SAP.

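### On Day 1, a non-serious reaction that starts between the required premedication and the first infusion is filed as medical history instead of as an adverse event (minor)

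*Protocol*

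**What the plan says.** **Premedication.** Section 1.6 states that "all patients must receive premedication with a corticosteroid, paracetamol/acetaminophen, and H1 and H2 blockers" before patisiran. Section 5.2.1 applies this to every patient and says of the four products that these "medicinal products should be given on the day of study drug infusion at least 60 minutes prior to the start of infusion". Three are listed as intravenous and paracetamol as oral, with oral equivalents allowed in some cases. Section 3.1 gives the same premedication to placebo patients to protect the blind. Section 5.2.3.1 uses the term study drug for patisiran or placebo, so premedication is a separate and earlier step.

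**Recording.** Section 6.5.7.2 makes the investigator responsible for "recording non-serious AEs that are observed or reported by the patient after administration of the first dose of study drug". Between consent and that point, "Events occurring after signing of the ICF and before study drug administration will be captured as medical history". Section 6.1 uses the same Day 1 cut-off for updating medical history. After study drug, AEs that occur are recorded, and so are existing conditions that get worse: "baseline events that worsen after study drug administration, must be recorded as AEs". Serious events follow a different rule. The investigator is responsible for "recording SAEs that are observed or reported by the patient after the time when the informed consent is signed".

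**Definition and analysis.** Section 6.5.7.1 defines an AE by reference to a patient who has been given a medicinal product, with no causal link required. Section 7.2.8 makes the frequency of treatment-emergent AEs the primary safety parameter.

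**The concern.** The premedication is imposed by the trial. A patient who becomes hypotensive or sedated after it, while waiting for the first infusion, is reacting to medicines taken because of enrolment. Medical history is meant for conditions a patient brings into a study, so filing the reaction there misdescribes it.

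The rule also classifies the same reaction by dose number. It is history before dose 1 and an AE before dose 2. The first exposure to the premedication is when an intolerance would first be expected to show. The protocol does anticipate intolerance: Section 5.2.1 allows the steroid to be lowered if poorly tolerated, and allows oral equivalents for agents not tolerated intravenously. At stake is whether the AE record for Day 1 is complete and described correctly.

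**Working it through.** The plan gives no figure to reproduce. The check is a timeline, followed by a count of how much of the premedication experience is affected.

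1. Let T be the start of the first infusion on Day 1. Premedication is given at T minus 60 minutes or earlier (Section 5.2.1). The only stated limit on how early is that it falls on the same day.
2. Non-serious AE recording begins once the first dose of study drug has been given (Section 6.5.7.2). Four protocol-required medicines have therefore been on board for at least 60 minutes before the window opens.
3. The recording rules then sort events as follows.

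| Event | Recorded as |
|---|---|
| Non-serious, starts after first premedication and before T, does not worsen later | Medical history |
| Same onset, worsens after study drug | AE |
| Non-serious, starts after first study drug, whatever its cause | AE |
| Reaction to premedication at dose 2 or later, including a return of a resolved Day 1 reaction | AE |
| Serious, any time after consent | SAE |

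Only the first row is a gap.

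4. Set that row against the definition. Section 6.5.7.1 requires an untoward occurrence in a patient given a medicinal product, and Section 5.2.1 calls the premedications medicinal products. The event meets the definition but falls outside the collection window.
5. The separate instruction to record all infusion-related reactions as AEs does not close the gap. Section 10.3 describes these as usually arising during or shortly after the infusion, and here no infusion has begun.
6. A patient who reacts and never starts the infusion would also fall outside the Safety Analysis Set, which requires some study drug (Section 7.2.1).

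**Count.** Double-blind dosing is on Day 1 and every 3 weeks from Week 3 to Week 51, so there are 51/3 + 1 = 18 premedication occasions. One is affected: 1/18 = 5.6% of occasions. With about 300 patients that is about 300 intervals of at least 60 minutes. This measures the window, not the reactions missed.

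**Number of reactions.** The documents give no rate for reactions in that interval. If 1% to 3% is assumed purely for illustration, the result is 300 × 0.01 = 3 to 300 × 0.03 = 9 patients. Nothing in the protocol supports that range.

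**Version.** The wording is the same in the original protocol and in Amendment 1. The Amendment 2 summary of changes lists no change to when AE recording starts, but the body of that amendment was not available, so its current text is presumed unchanged and not confirmed.

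**The case against.** The strongest defence is that the rule is coherent. Section 2 states the safety objective as the safety and tolerability of patisiran, and Section 6.5.7.1 asks about causality for study drug alone. An event before any patisiran or placebo cannot have been caused by it. Sections 6.1 and 6.5.7.2 share one cut-off, and a definition of an AE does not by itself fix when collection begins. The events are still written down, as history, and serious ones are captured from consent. All of this stands. It means the rule does not undermine the evaluation of patisiran. It does not make a reaction to a trial-imposed medicine a piece of medical history.

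Two stronger readings are tempting, and the documents support neither.

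- A reader might infer that a Day 1 reaction becomes a baseline condition, so that unchanged recurrences at later doses need not be recorded and an intolerance could vanish from the AE tables. Section 6.5.7.2 does not say that. Its worsening clause is an addition to the separate requirement to record AEs that occur after study drug, regardless of relationship. Section 6.5.7.1 also asks for the start and stop of each incidence of an intermittent AE. A reaction that resolves on Day 1 and returns at Week 3 is a new AE.
- A reader might infer that the comparison of arms is distorted. Both arms receive the same premedication, and the interval precedes study drug in both, so no such bias is shown.

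**Conclusion.** The point holds as a narrow misclassification, and its severity is minor. One pre-infusion interval per patient lies outside non-serious AE recording although protocol-required medicines have already been given. The affected events are non-serious, start in that interval and do not worsen afterwards. The consequence is an incomplete account of first-exposure premedication reactions in absolute terms, in both arms. The number of such reactions cannot be calculated from the documents.

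The conclusion rests on two readings: that study drug excludes premedication, which the protocol's usage supports throughout, and that the Amendment 2 text keeps the same start point, which its summary of changes suggests but does not prove. It does not rest on any claim about the safety objective, which concerns patisiran and not the premedication.

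**What to change.** In Section 6.5.7.2, start non-serious AE recording at the first protocol premedication or study drug on Day 1, whichever is earlier, and end the medical-history period at the same moment. Align the medical-history sentence in Section 6.1. List AEs that start before the first infusion separately, including those of any patient who is premedicated but never infused, so that the treatment-emergent comparison in Section 7.2.8 still starts at study drug.

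The change needs two protocol sentences, a matching line in the CRF completion guidelines and a date rule in the SAP. It alters no dose, schedule or clinical decision. The only downside is a few more AEs listed in both arms.

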6.5.7.3. Reporting Adverse Events of Clinical Interest to Sponsor/Designee

Not applicable. There were no AEs of Clinical Interest identified for this study.

6.5.7.4. Serious Adverse Events Require Immediate Reporting to Sponsor/Designee

An assessment of the seriousness of each AE will be made by the Investigator. Any AE and laboratory abnormality that meets the SAE criteria in Section 6.5.7.1 must be reported to the Sponsor or designee within 24 hours from the time that clinical study center staff first learns of the event. All SAEs must be reported regardless of the relationship to study drug.

The initial report should include at least the following information:

- Patient's study number
- Description and date of onset of the event
- Criterion for serious
- Preliminary assignment of relationship to study drug, and
- Investigator/site information

To report the SAE, complete the eCRF and, as applicable, the SAE form. Within 24 hours of receipt of follow-up information, the Investigator must update the eCRF and, as applicable, the SAE form. SAEs must be reported using the contact information provided in the Study Reference Manual.

Appropriate remedial measures should be taken by the Investigator using his/her best medical judgment to treat the SAE. These measures and the patient's response to these measures should be recorded. All SAEs, regardless of relationship to study drug, will be followed by the Investigator until satisfactory resolution or the Investigator deems the SAE to be chronic or stable. Clinical, laboratory, and diagnostic measures should be employed by the Investigator as needed to adequately determine the etiology of the event.

6.5.7.5. Sponsor Safety Reporting to Regulatory Authorities

The Sponsor or its representative will report certain study events in an expedited manner to the Food and Drug Administration, the European Medicines Agency's EudraVigilance electronic system according to Directive 2001/20/EC, and to all country Regulatory Authorities where the study is being conducted, according to local applicable regulations.

6.5.7.6. Serious Adverse Event Notification to the Institutional Review Board/Independent Ethics Committee

Suspected unexpected serious adverse reactions (SUSARs) will be reported to the IRB/IEC per their institutional policy by the Investigator or Sponsor (or Sponsor designee) according to country requirements. Copies of each report and documentation of IRB/IEC notification and acknowledgement of receipt will be kept in the Investigator's study file.

